## **IV. Research Methods**

### **A. Outcome Measure(s):**

During both the pre-PMC and post-PMC training periods, a trained Certified Nursing Assistant (CNA) (blinded) will assess gait speed, TUG, and SPPB within 24-48 hours of admission to SNF. If the CNA is unable to assess within 24-48 hours of admission, then the physical therapist performs the assessments. The occupational therapist will administer the Mini Mental Status Scale to assess baseline cognitive status within 24-48 hours of admission to SNF. A trained CNA (blinded) will continue to perform functional assessments (gait speed, TUG, SPPB) weekly and at discharge from SNF (Figure 2). Physical therapists (PTs) and physical therapist assistants (PTAs) will perform weekly and discharge assessments as necessary.

Interventions: During the 5-month pre-PMC training period (baseline), all current patients at the SNF will receive usual care treatment as facility therapists will practice per current standard of care. We will collect pre-PMC training data for 3 months or until collection of data on 602 patients (half the number of patients approved to be consented) (Figure 1). Therapists will then be trained on the PMC intervention for 2 months. After training, the facilities and individual therapists will decide how to implement such care at their discretion. Following the training period, we will collect post-PMC training data for 5 months or until collection of data on 602 patients (half the number of patients approved to be consented) (Figure 1). The data collected in all facilities during the pre-PMC training period will be pooled into one group to dilute the effect of facility variability. The data collected during post-PMC training period will be pooled in the same way.

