### C. Study Design and Research Methods

This study is a preliminary investigation using a pre-post training design in six SNFs (Figure 1). We will pool the data across the six SNFs into the pre and post-PMC training periods to dilute the effect of facility variability. Given that the average length of stay in a SNF is 21 days, the pre/post PMC training design will consist of two independent samples of patients to include only those that were admitted and discharged within a given period. As we get interest from additional facilities, we may submit an addendum to include them. Additional sites would help inform sample size estimates for a potential future, cluster-randomization study design. During the 5-month pre-PMC training period, the rehabilitation therapists will treat patients per the current standard of care and a trained CNA (blinded) or PT/PTA (as necessary) will collect outcomes data at admission, weekly, and at discharge. Then, training on the PMC intervention will occur over a 2-month period. Any patients admitted or discharged in the SNF during the PMC training period will not be used. During the 5-month post-PMC training period, therapists will implement the PMC protocol and collect outcomes data as indicated previously (Figure 1).

The medical records will provide information on prior level of function, age, other medical conditions, **re-hospitalization** and **emergency room visits**, medications, sex, admitting diagnosis, **falls**, SNF length of stay, **discharge location**, evaluation and treatment documentation.

Five focus group discussions of 4-6 therapists each will follow an interview guide and last a duration of approximately 1 hour. Therapist participation is voluntary, and all participants will be asked for informed consent. Discussions will be recorded and transcribed for content analysis.

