### Sample Size Estimates

Statistical power was estimated based on the results of a home-health pilot study of 22 participants: 10 were randomized to PMC, 12 to the usual care interventions. The home health population is similar to the SNF population given both experienced a recent acute hospitalization and subsequent decline in function. However, we anticipate patients in SNF will have less gain in gait speed compared to home health participants because the significant decline in function demonstrated in the patients in SNFs has rendered them unable to manage in the home. Therefore, we used the following results for the power analysis: means  $\pm$  standard deviations (SD) of  $0.31 \pm 0.29$  feet for PMC and  $0.13 \pm 0.12$  for usual care. For the power analysis we used a SD of 0.29 and mean difference of 0.14, which is the midpoint between 0.1 (clinically significant difference) and 0.18 (the difference

of the means of from the home health study). Thus, a sample size of 184 patients completing the study (92/group) will provide 90% power (**assuming the same SD in both groups to be conservative**) to detect differences at least that great. This estimate is conditional upon using a 1-sided, alpha = 0.05 level 2-group t-test.

. Of the sites currently listed under COMIRB 14-2388, we have not begun collecting data at Powerback Rehabilitation. Powerback is a growing facility that, on average, provides rehabilitation services to 120 patients a day. Approximately 2/3 of patients will likely be appropriate for the intervention; thus, across a 10-month data collection phase, we will require an increase in enrollment numbers to 800. Our current number approved is 434, so a total of 1,234 is being requested for approval to accommodate the large numbers of patients being seen for rehabilitation at Powerback. While this exceeds our initial sample size estimates, each facility has more variability than we anticipated (e.g., patient population, ratio of PTs to PTAs, rehab coverage on weekend, in house vs contracted rehab services). Therefore, additional facilities are necessary to better determine the variability of patient outcomes across different types of facilities for a future, multi-site pragmatic clinical trial. Furthermore, anticipated funding through the VA requires us to include facilities with Veterans (e.g., Veterans Community Living Center at Fitzsimons).

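### A 602-patient stop with no facility quota, combined with an unadjusted pooled test, lets facility shares differ before and after training; separately, the 800 for Powerback has no turnover step

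*Combined protocol and SAP*

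**What the plan says.** Section IV.A (Interventions paragraph) ends each period at a time limit or "until collection of data on 602 patients (half the number of patients approved to be consented"). The time limit attached to that rule is 3 months before training and 5 months after it. The opening section, the start of the same paragraph, and sections IV.B and IV.C all give 5 months before training. No section sets a ceiling by facility.

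Sample Size Estimates (section IV.F) explains the enrolment. Powerback, on average, "provides rehabilitation services to 120 patients a day". Then: "Approximately 2/3 of patients will likely be appropriate for the intervention", and "across a 10-month data collection phase, we will require an increase in enrollment numbers to 800". The request follows: "Our current number approved is 434, so a total of 1,234 is being requested for approval".

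On timing, the same section says that, of the listed sites, "we have not begun collecting data at Powerback Rehabilitation". Section IV.C adds: "As we get interest from additional facilities, we may submit an addendum to include them".

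On turnover, section IV.C begins its reasoning with "Given that the average length of stay in a SNF is 21 days" and counts only stays that start and finish inside one period.

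The Data Analysis Plan (section IV.F) pools all facilities within each period and compares mean change in gait speed by an independent-samples t-test. It has no facility term, and the conclusion rests on that one test. Sample Size Estimates reports that facilities vary more than expected in patient mix, staffing ratio, weekend cover and how therapy is contracted.

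**The concern.** A pooled pre/post comparison isolates the effect of training only if the facilities supply both periods in about the same proportions. The plan relies on pooling to dilute facility variability. Pooling does that when shares are equal; when they differ, it turns facility differences into an apparent programme effect.

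Nothing in the plan holds the shares equal. The stop is one count for all sites, sites do not all start together, more may be added, and the primary test cannot absorb a change of mix. The plan's own figures make Powerback 800/1,234 = 65% of all patients, so when that one site starts and stops largely sets the mix.

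The 800 matters because it feeds the total from which the stop is derived. If it understates intake, the count rather than the calendar may end a period.

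**Working it through.** **1. The plan's figures.** 120 × 2/3 = 80 eligible patients present on a day. 80 × 10 = 800, and 434 + 800 = 1,234. All reproduce. The factor of 10 treats 80 present on a day as 80 new patients a month. Half of 1,234 is 617, not 602. Since 602 × 2 = 1,204 = 1,234 − 30, the stop fits if the 30 therapists of section IV.B are subtracted, but the plan does not say so.

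**2. Adding turnover.** In steady state, admissions per month = 80 × 30.44 / stay. Stays that begin and end inside a 5-month window (152.2 days) = 80 × (152.2 − stay) / stay. At 21 days:

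- 80 × 30.44 / 21 = 116 admissions a month, or 1,160 in 10 months.
- 80 × (152.2 − 21) / 21 = 500 in-window stays, or 1,000 over two windows.

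**3. When 602 is reached.** Assume that all sites run together, that the others supply 434/2 = 217 per period (43.4 a month), and that stays are equal everywhere. At 21 days:

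- By admissions: 602 / (116 + 43.4) = 3.8 months.
- By completed stays: 602 / (80/21 + 43.4/30.44) + 21 = 136 days = 4.5 months.

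No Powerback stay is given, so the range is:

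| Stay (days) | Powerback admissions, 10 months | In-window stays, two windows | 602 reached, by admissions (month) | 602 reached, by completed stays (month) |
|---|---|---|---|---|
| 14 | 1,739 | 1,579 | 2.8 | 3.2 |
| 18 | 1,353 | 1,193 | 3.4 | 4.0 |
| 21 | 1,160 | 1,000 | 3.8 | 4.5 |
| 25 | 974 | 814 | 4.3 | 5.1 |
| 30.4 | 800 | 640 | 4.9 | 5.9 |
| 35 | 696 | 536 | 5.3 | 6.5 |

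Counted by completed stays, the stop no longer binds within 5 months from about 25 days upward.

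**4. The 3-month reading.** At 21 days, 3 months give 3 × (116 + 43.4) = 478 admissions, so a 3-month pre-period ends by calendar. Five months would give 797 admissions or 687 in-window stays, so the post-period ends by count. The two periods would then close under different rules.

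**5. Effect of a different mix.** Apparent effect = (Powerback's post share − its pre share) × (difference in mean gain between Powerback and the rest). With all sites concurrent and intake steady, Powerback's share is 116 / 159.4 = 73% whether or not the stop binds, and the apparent effect is zero.

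For illustration, let Powerback enter one period late and the other on time (21-day stay, counted by admissions). Assume a 0.10 difference in mean gain, in the units of the power calculation, and use the plan's SD of 0.29:

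| Months late | Patients in that period | Powerback share | Share difference | Apparent effect | In SE |
|---|---|---|---|---|---|
| 1 | 602 | 67.5% | 0.052 | 0.005 | 0.31 |
| 2 | 565 | 61.6% | 0.112 | 0.011 | 0.66 |
| 3 | 449 | 51.7% | 0.211 | 0.021 | 1.17 |

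SE = 0.29 × √(1/602 + 1/n), with n the number in the late period: 0.0167, 0.0170 and 0.0181. The last two effects are 8% and 15% of the 0.14 design difference. The delays and the 0.10 are assumptions. The shift comes mainly from timing: with a 1-month delay the share is 67.5% with the stop and 68.1% without it.

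**The case against.** Several objections have force.

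**The stop alone does not change the mix.** This stands, as step 5 shows. The opening section does describe concurrent running, but for two facilities; the plan now has six, one of which had not started. If every facility has its own windows, a late start is the same in both periods and does no harm. The documents do not say whether windows are set by facility or study-wide.

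**A reader might infer that a late site could find the post count already full and supply usual-care patients only.** The documents do not support this. For Powerback, the previously approved number was 434 over both periods, which cannot fill a post count of 602. Any later site needs an addendum. The one recorded increase raised the approved number from 434 to 1,234, and a stop defined as half that number would rise with it. Whether every addition brings an increase is not stated, so the scenario is speculative.

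**A reader might take the 800 as a proven error.** It is not. A Powerback stay near 30 days, or capture of about 800/1,160 = 69% of eligible admissions, also gives 800. Neither is in the documents, but neither is excluded; the 21 days is a general average.

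**A reader might infer that enrolment is too low or power is threatened.** Neither follows. A time-or-count rule expressly lets the count end collection, the 800 may be meant as a ceiling, and 602 is more than six times the 92 per group required. The plan says the excess serves a future trial.

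That the stop is study-wide is itself an inference, from its link to the approved total and the absence of any facility quota. It is the natural reading.

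**Conclusion.** The concern holds as a risk to comparability. The plan combines a stop with no facility quota, staggered sites, acknowledged facility differences and an unadjusted pooled test, and has no safeguard against unequal facility shares. Whether shares will differ, and by how much, depends on timing and intake that the documents do not give. The effects of 0.005 to 0.021 are illustrations, not estimates, and could run in either direction.

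Separately, the 800 lacks a stated length-of-stay or capture assumption. At 21 days it would be about 1,160 admissions or 1,000 in-window stays, and a 5-month period could end at about 3.8 to 4.5 months if the other sites supply 217. Longer stays weaken this, and a 3-month pre-period would not reach the stop at that rate. The point deserves correction, but it does not show that the study will be biased or underpowered.

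**What to change.** 1. Apply the stop by facility, with the same window length and the same ceiling in that facility's pre and post periods.
2. Include in the pooled primary comparison only facilities that complete both periods.
3. Stratify or adjust the primary comparison by facility. Equal ceilings do not guarantee equal shares, because a facility may reach its ceiling in one period only, and the opening section reports census varying from month to month.
4. Restate the 800 with its length-of-stay or capture assumption, or label it a ceiling. As a ceiling of 400 per period at a 21-day stay, it would be reached at about 400 / 3.81 + 21 = 126 days (4.1 months).
5. Reconcile the 3-month pre-period in section IV.A with the 5 months stated elsewhere, and reconcile 602 with half of 1,234.

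The cost is protocol and analysis-plan wording and, for six facilities, five extra model terms. No extra patients are needed. The downside is that a facility with only one period is left out of the pooled comparison, although its data can still be described for planning the later trial.

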### G. Summarize Knowledge to be Gained:

Rehabilitation therapy is known to help improve function in older adults after an acute functional decline. However, we do not know if there is an additional benefit to implementing a progressive program with an emphasis on activity throughout the day in the SNF setting. Effective rehabilitation interventions in SNFs can improve function in adults, which allows patients to return to prior level of care and location. This study has the potential to not only improve individual functional outcomes but also increase community discharge rates and reduce hospital readmissions. The alternative treatment is to choose a different skilled nursing facility (non-research site) which employs a different standard of care.

